Starting with the population selected for Aim 1, we will create a sub-population by matching patients referred to a cardiology specialist (the primary outcome variable for Aim 1) to similar non-referred patients. The goal of this matching is to balance factors that may be confounders of the relationship between referral and cardiovascular outcomes. We will identify factors found to be associated with cardiology referral from Aim 1, as well as factors that are expected to be associated with outcomes such as, age, race, insurance status/type, ASCVD risk score, and comorbidity index. We will not seek to match on factors that may be associated with referral but unlikely to be directly associated with outcomes. For example, we may not want to match on cardiologist availability by site if this is only related to referral and not independently to outcomes. Variables that potentially modify the effect of referral (e.g., sex, race/ethnicity, insurance status) will be included among the matching factors. Patients will be matched within sites and year of baseline encounter.

For each patient referred to a cardiologist we will identify one non-referred patient (1:1 matching) within each site. We will match using values of the individual confounders, with an exact match on sex, race/ethnicity, insurance status/type, and to within a small caliper for continuous variables (e.g., ±5 years for age). Matched pairs will be identified using optimal matching. If this approach fails to identify an adequate number of matched pairs, then 1:1 matching will be implemented using a propensity score.

Once the matching has been implemented, the same baseline characteristics reported for Aim 1 will be summarized in the matched cohort by referral status. Metrics (e.g., standardized differences) will be reported to evaluate how well-balanced the referred and non-referred groups.

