For this aim, the primary outcome variable will be blood pressure control based on prevailing guidelines during the study period (blood pressure <140/90 mmHg). The co-primary outcome is lipid control, defined by prevailing guidelines during the study period. These outcomes will be evaluated longitudinally during 5-years of follow-up. Secondary outcome variables include time to the first major adverse cardiovascular event (MACE = cardiovascular death, myocardial infarction (MI)), stroke, heart failure hospitalization, peripheral artery disease procedure, coronary artery disease (based on diagnosis codes or coronary artery revascularization procedure), and all-cause death. Events ascertained from relevant diagnosis and procedure codes, and from a query of the National Death Index Plus, State Death records, Social Security Death Masterfile, Hospital death record and/or similar death record for causes of death including cardiovascular

death. We will also evaluate time to BP control and time to lipid control among patients who were not controlled at study start. For this Aim, "time zero" for the matched patient pair will be defined as the time from baseline (see Aim 1) when the referred patient kept their cardiology appointment. Events will be ascertained starting from time zero and until the end of follow-up. For each patient, end of follow-up will be defined as the date of the last outcome event or health system encounter without an event, occurring ≥3 months prior to the retrospective study review period of December 31, 2020 of the EHR.

To evaluate the association between cardiology referral and subsequent blood pressure and lipid control (coprimary outcomes), we will first evaluate these measures between referred and non-referred patients at baseline, and then compare prevalence and time trends between referred and non-referred patients using methods appropriate for longitudinal data analysis. For example, we will explore whether the proportion of patients with adequately controlled BP at each year is higher in referred compared to non-referred patients. Because these analyses are conducted in the matched population, the results are adjusted for the potential confounders included in the identification of the matched pairs.

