To evaluate the association between cardiology referral and CVD events (secondary outcomes), the cumulative incidence of primary and secondary outcomes will be summarized in the referred and matched non-referred patients. Follow-up will be censored at the earliest of 8 years or end of follow-up. For each outcome variable a Cox regression model will be fit, and the hazard ratio (referral vs. not referred) and 95% CI, and p-value will be reported. The Cox regression analysis will account for the matched pairs design using the empirical sandwich variance estimate. Statistical significance will be determined at the two-sided 0.05 level.

The relationship between referral status and outcomes will also be evaluated within subgroups of primary interest: sex, race, ethnicity and insurance as defined in Aim 1. Evidence for a differential association between referral status and CVD outcomes for different subgroups will be quantified using an interaction test in the Cox regression analysis. The considerations and approaches outlined in Aim 1 regarding missing data and sensitivity analyses will also be applicable for Aim 2.

#### 12.2.1 Expected power and sample size for Aim 2

Aim 2 expected power and sample size: With an anticipated cardiology referral rate of 20-25% among 1,200-1,500 patients included in Aim 1, the sample size in the matched cohort study is expected to be 250-375 per group. These patients will be accrued into the study over 5 years (2012-2016) and then followed to evaluate BP and lipid control, and for cardiovascular events for up to 8 years through December 31, 2020. For the primary endpoints, the rates in the non-referred group are anticipated to be 30% and 45% for BP and lipid control, respectively. With 300 per group, the study is predicted to have >70% power to detect a 10% increase in rate of BP control, and >95% power to detect a 15% increase in rate of lipid control due to cardiology referral. For the secondary endpoints, the rate of MACE events is anticipated to be fairly low (i.e., a cumulative incidence ~5% at 5 years and ~10% at 10 years) and we anticipate modest power to detect even large reductions in risk of CVD events due to cardiology referral. However, this aim will provide useful information about clinical event rates and estimates of the potential to effect event rates that could be attributed to cardiology referral.

#### 12. 3 Analysis Plan for Aim 3

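### Time to BP or lipid control is analysed in patients uncontrolled at an undefined study start, with no adjustment for the starting value and no balance check in that subset

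*Combined protocol and SAP*

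**What the plan says.** Section 12.2 (Analysis Plan for Aim 2) builds the cohort by pairing: "For each patient referred to a cardiologist we will identify one non-referred patient (1:1 matching) within each site". Pairs are formed within site and year of the baseline encounter, "with an exact match on sex, race/ethnicity, insurance status/type, and to within a small caliper for continuous variables (e.g., ±5 years for age". The remaining matching factors come from two sources. One is data-driven: "We will identify factors found to be associated with cardiology referral from Aim 1". The other is an open list of "factors that are expected to be associated with outcomes such as, age, race, insurance status/type, ASCVD risk score, and comorbidity index". Neither BP control nor lipid control is named. They are also not among the candidate patient and provider factors in section 12.1, where blood pressure and cholesterol appear as baseline characteristics to be summarised.

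The analysis at issue is one sentence: "We will also evaluate time to BP control and time to lipid control among patients who were not controlled at study start". The next sentence sets time zero for a pair at the referred patient's kept cardiology appointment, and events count from there. Section 12.1 allows 6 months from baseline to referral and 3 more months to the visit.

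On adjustment, section 12.2 says of the co-primary comparison that results are adjusted because they come from the matched population. The Cox paragraph reports one hazard ratio per outcome, referred versus not, and adds: "The Cox regression analysis will account for the matched pairs design using the empirical sandwich variance estimate". It lists no covariates. No separate model is given for time to control, so I take this one to apply. Standardized differences are planned for the matched cohort; none are described for the uncontrolled subset.

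**The concern.** Matching balances the two groups as they were matched. Restricting afterwards to uncontrolled patients keeps one member of a pair and may drop the other, so the claim that matching supplies the adjustment is not secured in the subset. The sandwich variance corrects standard errors for pairing; it does nothing about imbalance.

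Two things are then at stake for the hazard ratio. First, how far a patient starts above the threshold strongly affects how soon control is reached. If that distance differs between referred and non-referred patients, the difference enters the hazard ratio directly. Second, if status is set at the Aim 1 baseline but the clock starts at the visit, some patients count as reaching control when they had already done so before time zero. Index is the date a threshold is first met on a risk score that can include systolic BP (section 7.3.1), which favours chance-high readings that later settle.

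**Working it through.** **1. The plan's own figures.** Section 12.2.1 says "the rates in the non-referred group are anticipated to be 30% and 45% for BP and lipid control, respectively" and claims more than 70% power for a 10-point gain in BP control and more than 95% for a 15-point gain in lipid control, at 300 per group and two-sided 0.05. With p̄ the mean of the two rates, power = Φ{[d − 1.96·√(2p̄(1−p̄)/n)] / √[(p1(1−p1)+p2(1−p2))/n]}.
- BP, 30% vs 40%: (0.10 − 0.0763)/0.0387 = 0.611, power 72.9%.
- Lipid, 45% vs 60%: (0.15 − 0.0799)/0.0403 = 1.739, power 95.9%.

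Both agree with the plan. The plan gives no figure for lost partners and no baseline control rate.

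**2. Lost partners.** Assumption: the 30% and 45% also hold at start in both groups. With u the uncontrolled share, the loss among those analysed is 1 − P(both uncontrolled)/u.
- Independent within pairs, BP: 300×0.70 = 210 per group; 300×0.70² = 147 intact pairs; 63/210 = 30%.
- Independent within pairs, lipid: 300×0.55 = 165 per group; 300×0.55² = 90.75, about 91 intact pairs; 45%.

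Matching on the ASCVD score makes positive correlation within pairs likely. From a bivariate normal model:

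| Within-pair correlation (assumed) | BP: P(both), loss | Lipid: P(both), loss |
|---|---|---|
| 0.2 | 0.515, 26% | 0.334, 39% |
| 0.4 | 0.542, 23% | 0.367, 33% |
| 0.6 | 0.573, 18% | 0.404, 27% |

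If the referred group's starting control rate differs, the loss under independence is 1 − 2·u_ref·u_non/(u_ref + u_non). For BP with 20% of the referred group controlled: 1 − 2(0.80×0.70)/1.50 = 25%; with 40%: 1 − 2(0.60×0.70)/1.30 = 35%. For lipids with 35%: 1 − 2(0.65×0.55)/1.20 = 40%; with 55%: 1 − 2(0.45×0.55)/1.00 = 50.5%.

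**3. What this does to balance.** Simulation, with all inputs assumed: log-odds of referral rise 0.2-0.3 per SD of the starting value; exact matching on one factor correlated 0.3-0.6 with it; 30-45% controlled at start.
- Imbalance created in the matching factor within the subset: about 0.03-0.07 SD.
- Difference in starting value within the subset: about 0.05-0.14 SD.
- For comparison, with no matching and 30% controlled, the starting-value difference is 0.10-0.15 SD among the uncontrolled and 0.20-0.30 SD in the whole cohort. The restriction narrows this gap; its source is that BP or lipid level is not itself matched.

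**4. The clock.** If study start means the Aim 1 baseline, time zero can fall 6 + 3 = 9 months later. Take two readings with no true change, the plan's 30% and 45% control rates at both, and a within-person correlation of 0.5-0.8 (assumed). The share uncontrolled at the first reading and controlled at the second is again 1 − P(both)/u.
- BP: correlation 0.8, 1 − 0.611/0.70 = 13%; correlation 0.5, 1 − 0.557/0.70 = 20%.
- Lipid: correlation 0.8, 1 − 0.448/0.55, about 18%; correlation 0.5, 1 − 0.385/0.55 = 30%.

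**The case against.** A reader might infer that with 30-45% of patients lacking a partner the comparison is no longer matched. The documents do not support that. The Cox model described is not stratified by pair, so single members contribute legitimately, and confounding control depends on balance between groups, not on both partners being present. Balance in the matching factors fails only if control status differs by referral given those factors, and step 3 suggests a small effect. Even under independence, 55-70% of those analysed keep their partner. Nor is 30-45% a documented loss: it takes anticipated non-referred endpoint rates as baseline rates in both groups and ignores correlation within pairs.

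Three further objections have force. The list of matching factors is open, so control status can be called not named, but not excluded. The named ASCVD score draws on systolic BP, cholesterol and hypertension treatment (section 7.3.1), so there is some indirect matching. And section 12.2 will compare BP and lipid control between groups at baseline and report standardized differences, though for the full matched cohort. Indirect matching remains partial, because equal scores can arise from different mixes of age, smoking, diabetes and BP.

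On timing, study start could be meant as time zero. The early-control problem would then disappear. The documents support only that the term is undefined. Chance-high index readings would also occur in both groups, so a differential effect is not shown.

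**Conclusion.** The point holds as a minor one about an additional analysis. The plan does not define when uncontrolled status is set, states no adjustment for the starting BP or lipid value, and describes no balance check in the subset it analyses. The sizes that matter are a possible starting-value difference of about 0.05-0.14 SD and, only if study start is the Aim 1 baseline, 13-20% (BP) or 18-30% (lipid) of patients already reading as controlled at time zero. Both rest on assumed slopes and correlations, not on figures in the documents. Partner loss describes the subset and should not be read as a measure of bias. The co-primary longitudinal comparison uses the full matched cohort and is not affected.

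**What to change.** Amend section 12.2 as follows.
- Define uncontrolled status at the pair's time zero, for both members, using readings taken before it.
- Fit the time-to-control Cox model with the starting BP or lipid value and the matching factors as covariates, keeping the sandwich variance.
- Report standardized differences by referral status within each uncontrolled subset.
- Optionally, repeat the analysis in pairs where both members are uncontrolled, as a sensitivity analysis. Under step 2 with independence, that leaves about 147 pairs for BP and 91 for lipids.

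The cost is SAP wording and a few covariates from data already being extracted. The downside is that patients with no reading before time zero drop out of this additional analysis; their number should be reported by group.

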Then, DCRI will take the query data that the sites provide to identify and further stratify data for potential cohort of patients, based on additional clinical characteristics. At the earliest clinical contact within look back period, we will identify HIV status according to ICD9/10 codes and prescription of ART. We will include individuals >18 years of age and < 99 years of age, plus will ascertain time-updated data for the following potential characteristics:

hemoglobin, creatinine (or glomerular filtration rate), age, sex, race, ethnicity, insurance status, total cholesterol, HDL cholesterol, LDL cholesterol, systolic blood pressure, prescription of anti-hypertensive medications, family history of coronary artery disease, presence of diabetes, previous diagnosis of any acute myocardial infarction, hospitalization for heart failure, acute coronary syndromes, stable or unstable angina, arterial revascularization, stroke, transient ischemic attack and peripheral arterial disease presumed to be of atherosclerotic origin determined by ICD9/10 codes. Behavioral factors are smoking status, number of clinic visits per year, length of time between clinic visits and missed appointments with specialist after referral. Data will also be ascertained on HIV viral load, CD4 count, prescription of any ART and length of time on all medications. This list captures the majority of the data related to our scientific aims and will be modified as the availability of these data are discovered.

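### Time to BP control has no common assessment grid, so extra readings in referred patients, starting with the time-zero visit, shorten it even if referral has no effect

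*Combined protocol and SAP*

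**What the plan says.** Section 12.2 makes BP control (below 140/90 mmHg) and lipid control (by the guidelines then in force) the co-primary outcomes, followed for 5 years. The comparison is of prevalence and time trends, with this example: "we will explore whether the proportion of patients with adequately controlled BP at each year is higher in referred compared to non-referred patients". The section then adds: "We will also evaluate time to BP control and time to lipid control among patients who were not controlled at study start".

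The rest of the design bears on how often control can be observed:

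- Readings are those recorded in routine care (Section 8.1). There are no study visits.
- A patient counts as referred only if the cardiology visit was kept (Section 12.1). That visit is time zero for the pair, and ascertainment starts there (Section 12.2).
- Matching is on baseline factors: "we will identify one non-referred patient (1:1 matching) within each site".
- Section 8.1 collects the "number of clinic visits per year", but Section 12.2 gives it no role in the outcome analysis.
- Section 12.2 carries over the sensitivity analyses of Section 12.1. One of these restricts to patients with routine follow-up, judged by a certain number of visits.

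The plan does not state which reading counts (any, last, mean or confirmed), what window surrounds each year, how a year without a reading is handled, or any method for unequal visit frequency or interval censoring.

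**The concern.** Without a schedule, time to control is in practice time to the first controlled reading on record. BP varies from visit to visit, so an uncontrolled patient who is measured more often will sooner have a reading below the threshold by chance. The referred group has a clinical contact at time zero by definition and may have further cardiology visits. The match inherits the date without the contact. Matching at baseline cannot equalise what happens after time zero. The minimum-visits sensitivity analysis sets a floor and is aimed at drop-out, so it does not equalise frequency either.

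The bias runs in the direction of the study hypothesis. The study could report that referral speeds BP control when the result only reflects more measurement.

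**Working it through.** **1. The plan's own power figures.** Inputs from Section 12.2.1: for the control rates, "the rates in the non-referred group are anticipated to be 30% and 45% for BP and lipid control, respectively". The section takes 300 patients in each arm and claims power above 70% for a 10-point gain in BP control and above 95% for a 15-point gain in lipid control. Test level: "Statistical significance will be determined at the two-sided 0.05 level". For two proportions with pooled variance under the null,

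power = Φ{[|p2 − p1|·√n − 1.96·√(2p̄(1 − p̄))] / √[p1(1 − p1) + p2(1 − p2)]}.

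- BP, 0.30 vs 0.40, n = 300: (1.732 − 1.96 × 0.6745) / 0.6708 = 0.611, so power is 72.9%.
- Lipids, 0.45 vs 0.60, n = 300: (2.598 − 1.96 × 0.7062) / 0.6982 = 1.739, so power is 95.9%.

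Both figures reproduce. The calculation treats control as one binary value per patient, so reading frequency does not enter it.

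**2. The mechanism in its simplest form.** If each reading is controlled with probability p, independently, the chance of at least one controlled reading in k is 1 − (1 − p)^k. With p = 0.30, this is 1 − 0.7³ = 66% for three readings and 1 − 0.7⁴ = 76% for four. Readings on one person are correlated, and time to control is restricted to patients who start uncontrolled, so this shows direction only.

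**3. Simulation with no effect.** Each reading is a person-level mean plus within-person noise, with 30% of all readings controlled. Only patients with an uncontrolled starting reading are kept: 70% of 300 = 210, taken as 200 per group. Readings arrive at random at a fixed yearly rate for 5 years, and a Cox model is fitted to the first controlled reading. There are 200 runs per setting. The reading rates, the correlation (0.3 or 0.5) and the Cox model for this outcome are assumptions. The day-0 rows also assume that starting status is set by an earlier reading; the plan ties study start to neither baseline nor time zero.

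| Readings a year, non-referred / referred | Day-0 reading in referred | HR, correlation 0.3 / 0.5 | Rejections at two-sided 0.05 |
|---|---|---|---|
| 3 / 3 | no | 0.99 / 0.99 | 4% / 6.5% |
| 3 / 3 | yes | 1.21 / 1.15 | 41% / 24% |
| 3 / 4 | yes | 1.42 / 1.30 | 92% / 64% |

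A separate simulation under the same kind of model gave 1.25 / 1.11 for the day-0 reading alone and 1.47 / 1.33 for 3 vs 4 plus day 0. Taken together, the ranges are about 1.1 to 1.25 and 1.3 to 1.5. Median time to control at 3 vs 4 plus day 0 is 1.15 vs 0.56 years (correlation 0.3) and 1.69 vs 0.99 years (0.5).

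The day-0 effect has a simple source. Among patients uncontrolled at start, any single later reading is controlled about 24–25% of the time at correlation 0.3 and 20–21% at 0.5. That share of referred patients reaches control at once, with no counterpart among the matches.

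**4. Yearly proportions under two reading rules.** Same runs, 3 vs 4 plus day 0, first year, among patients with a reading:

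- Any controlled reading counts: 49% vs 62% (0.3) and 40% vs 50% (0.5).
- Last reading counts: 24% vs 24% and 20% vs 20%. Rejection across all settings is 3–7.5%, within simulation error of 5%.

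**The case against.** The strongest reply is that the plan does not adopt a biased rule; it states no rule. The natural reading of control at each year is status at a time point, and the power calculation fits that reading. Time to control is an additional analysis, neither a co-primary outcome nor the basis of the sample size. This stands, and it limits the point. A reader might infer that the co-primary yearly proportions are themselves biased. The documents do not support that: step 4 shows no difference when one reading per window counts, apart from informative missing readings.

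A reader might also set the 10-point gap in step 2 beside the 10-point BP difference used for power. They are different quantities. One is ever controlled across several readings (66% vs 76%); the other is a single status per patient (30% vs 40%).

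The extra readings are an inference. The documents establish one kept cardiology visit. They do not show that later cardiology visits add to other visits rather than replace them, and a match may see a cardiologist later. So a lasting gap in frequency is an assumption. The time-zero contact follows from the design, and a BP reading there is likely. For lipids the inference is weaker, since a panel has to be ordered.

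History of keeping appointments is a candidate factor in Section 12.1 and could enter the matching. It might narrow a gap in attendance, but it would not remove the time-zero contact or equalise later readings.

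**Conclusion.** The point holds for time to BP control. As written, the analysis favours referral whenever referred patients are measured more often, and the time-zero visit alone is enough. Under no effect the hazard ratio is about 1.1 to 1.25 from the day-0 reading alone, and about 1.3 to 1.5 with 3 versus 4 readings a year plus day 0. These sizes rest on assumed reading rates, a within-person correlation of 0.3 to 0.5, and starting status fixed before time zero. The direction needs only that referred patients have more readings.

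For the yearly co-primary proportions the finding is conditional: biased if any controlled reading in the year counts, and not biased with one reading per window unless missing readings are informative. For lipids the mechanism is the same but its premise is less secure, and no size is claimed. Because time to control is an additional analysis, this should be settled before analysis but does not undermine the co-primary comparison as such.

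**What to change.** In Section 12.2, define control in both groups from one reading per fixed window after time zero, for example the last outpatient reading in each 12-month window, and exclude the reading from the time-zero visit. Treat a window with no reading as missing, not as uncontrolled; otherwise unequal measurement re-enters. State which reading fixes control status at study start, in the same way for both groups.

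Use this definition for the yearly proportions, and analyse time to control on the same grid with a discrete-time or interval-censored model. Report readings per patient-year by group, and add a sensitivity analysis weighted for the probability of being measured, since missing readings may be informative.

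The data are retrospective and visit counts are already collected, so the cost is SAP wording and some programming. The downside is that some readings go unused and event times become coarser.
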